## **INVESTIGATOR STUDY PLAN - REQUIRED**

### **1. TITLE**

Comparison of a standalone, continuous, non-invasive blood pressure monitor (cNIBP) to radial arterial catheterization in patients undergoing surgery.

### **2. EXTERNAL IRB REVIEW HISTORY\***

Device reviewed and accepted by Tufts IRB.

### **3. PRIOR APPROVALS:**

Prior approvals: Departments of Anesthesiology and Perioperative Medicine and Surgery

**Conflict of Interest (COI):** There are no individuals involved that have a financial interest related to this research.

#### **Clinical Engineering Department:**

This medical device will be inspected for safety, including grounding and minimal current leakage as necessary, prior to being placed in service. The Clinical Engineering Department Electrical Safety Inspection protocol shall be used as the inspection procedure. All measurements shall meet the NFPA 99, IEC 60601 healthcare standards for electrical safety.

We will notify the Clinical Engineering Department, at [contact] directly, or through the Materials Management Department, upon delivery of said equipment. The outside manufacturers/contractors are responsible for the quality and performance of all rented, leased, contracted, or equipment on evaluation.

#### **Biohazardous Agents:**

None

#### **Radiation:**

None

### **4. OBJECTIVES\***

The purpose of this study is to compare noninvasive and continuous radial artery blood pressure (BP) measurements over a wide range obtained by the ViTrack (a cNIBP device developed by Dynocardia) to that obtained from invasive radial artery catheterization in patients undergoing surgery or those who are being cared for in the intensive care unit (See Figures 1 and 2). As a precaution because Intensive Care Unit patients are at a higher risk for compromised skin, subjects that are admitted to the ICU will not wear this device for more than four hours while in the ICU. The BP will range from very low to very high and at a minimum will include BP ranges defined by ANSI/AAMI SP10-1992 standards: Low (SBP: 90-129 mmHg; DBP: 40-79 mmHg); Medium (SBP: 130-160 mmHg; DBP: 80-100 mmHg); and High (SBP: 161-180 mmHg; high DBP- 101-130 mm Hg).

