### **13. Data Analysis and Management\***

A minimum of 255 data points will be selected by random computer generator from each patient's arterial line and ViTrack recordings. The analysis of 255 time points per patient will be used to compare ViTrack with arterial line measurements. For each sample data point, a "ten beat epoch average" will be calculated, i.e. four beats prior and six beats after (including the sample point itself) will be averaged. Differences in device readings will be calculated as ViTrack minus arterial line values. In addition, Bland Altman plots will be used to determine agreement between the two devices. Our protocol will greatly exceed the AAMI guidelines by examining 255 paired measurements per patient for a minimum total of 5100 time points across 30 patients.

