## Statistical and Data Analysis Plan:

A total of n=30 patients were recruited to optimize the ViTrack technology and compare its performance to radial invasive arterial lines. A total of n=24 patients were used to optimize hardware, device form factor, algorithms, and usability. Then, we used the updated version of the ViTrack device to compare the device performance on 6 patients undergoing vascular surgery in the University of Massachusetts Medical School.

The data was analyzed following the AAMI SP10:2008 standard. Both ViTrack and Invasive arterial pressure data were averaged over a 20-second non-overlapping window, thus providing a paired measurement for comparison every 20 seconds. The average length of the surgery was ~3 hours. After clearing out the segments (both in IAP and ViTrack) affected by motion artifacts, we used the remaining segments for accuracy analysis. Since each dataset might not have a similar number of data points to compare, we weighted the samples to avoid bias to one dataset. A total of 2800 data points across 6 subjects were used for comparison. As per the FDA standard ANSI/AAMI SP10:2008 or the newly adopted ISO 81060-3:2022 standard, the mean error should be <5mmHg or <6mmHg and the standard deviation should be <8mmHg or <10mmHg respectively. We have analyzed ViTrack data on 6 patients and showed the results in **Figure 1** below. ViTrack showed far higher accuracy for both SBP (mean error = 0.19 mmHg [SD = 5.70 mmHg]) and DBP (mean error = 0.90 mmHg [SD = 5.97 mmHg]) measurements when compared to either of the recognized standards [**Fig1**].

**Fig 1: Performance of ViTrack Vs. IAP after motion artifact correction in 6 operating room patients undergoing vascular surgery.**

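### The protocol promises low, medium and high BP coverage, but no count, bias or slope by BP level is planned, so a large error in a sparsely sampled high band could go undetected

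*Protocol*

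**What the plan says.** Protocol section 4 (Objectives) sets out a comparison over a wide range of pressures and commits to coverage: "The BP will range from very low to very high and at a minimum will include BP ranges defined by ANSI/AAMI SP10-1992 standards". Numeric limits follow for three bands, the top one being "High (SBP: 161-180 mmHg; high DBP- 101-130 mm Hg".

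The later sections do not take these bands up:

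- Protocol section 10 (Study Endpoints) makes accuracy, judged by Bland-Altman plots, both the primary and the secondary outcome. It has no band element.
- Protocol section 13 (Data Analysis and Management) sets the sampling rule: "A minimum of 255 data points will be selected by random computer generator from each patient's arterial line and ViTrack recordings". There is no quota or stratum by pressure. It adds that "Bland Altman plots will be used to determine agreement between the two devices". The sample size of 1570 pairs is for agreement at all levels together.
- The SAP does not use the random draw. Readings are "averaged over a 20-second non-overlapping window, thus providing a paired measurement for comparison every 20 seconds", and all windows left after artifact clearing are kept. On weighting it says "we weighted the samples to avoid bias to one dataset", so weights follow the dataset and not the BP level.
- The SAP then states: "A total of 2800 data points across 6 subjects were used for comparison". It gives one mean error and SD for SBP (0.19, SD 5.70 mmHg) and one for DBP (0.90, SD 5.97 mmHg). It sets these against limits of 5 or 6 mmHg for the mean and 8 or 10 mmHg for the SD.

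**The concern.** The objective is about a range of pressures, while the summary that decides success is an average over whatever pressures happened to occur. Neither document asks how many points or patients fell in each band, what the error was there, or whether error changes with BP level. The SAP text does not say whether any of the 6 patients reached the high band.

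A pooled mean and SD mostly reflect the commonest pressures. If the high band is sparse, an error confined to it moves both figures only slightly. An error that runs in opposite directions at low and high pressure cancels in the mean. Section 4 of the protocol calls for further optimisation of the algorithm if bias exceeds the standards, and a bias that averages out would not trigger that step. The wide-range objective could then be taken as met without evidence that the range was covered or that accuracy held across it.

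**Working it through.** **The plan's own figure.** Inputs from protocol section 13: alpha 0.05, beta 0.1, expected mean difference 5, SD 10, maximum allowed difference 26 mmHg. The normal approximation for Bland-Altman limits is

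n = (z₀.₉₇₅ + z₀.₉₀)² × SD² × (1 + 1.96²/2) / (26 − 5 − 1.96 × 10)²

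With unrounded quantiles this is 10.507 × 100 × 2.921 / 1.961 = 1565. A non-central t version gives 1568, with power 0.900 at n = 1570. The stated 1570 therefore reproduces. BP level does not enter the calculation.

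**What the pooled result can hide.** Let f be the (weighted) share of points in the high band, d the gap in mean error between that band and the rest, and s a common within-band SD. Then

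- pooled mean = f × e_high + (1 − f) × e_rest
- pooled variance = s² + f(1 − f)d²

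The pooled means and SDs are the SAP's. The documents give neither f nor s, so both are assumptions shown over a range.

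*Working back from the reported SBP result, f = 5%:*

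- s = 5.0: d = √[(5.70² − 5.0²)/(0.05 × 0.95)] = √(7.49/0.0475) = 12.6; e_high = 0.19 + 0.95 × 12.6 = 12.1; e_rest = −0.44.
- s = 5.5: d = √(2.24/0.0475) = 6.9; e_high = 0.19 + 0.95 × 6.9 = 6.7.
- With the opposite sign (under-reading), e_high is −11.7 and −6.3.

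High-band mean error (mmHg, positive solution) compatible with the reported pooled figures:

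| Share f | SBP, s = 5.0 | SBP, s = 5.5 | DBP, s = 5.0 | DBP, s = 5.5 |
|---|---|---|---|---|
| 2% | 19.3 | 10.7 | 23.7 | 17.2 |
| 5% | 12.1 | 6.7 | 15.1 | 11.0 |
| 10% | 8.4 | 4.7 | 10.7 | 7.9 |
| 20% | 5.7 | 3.2 | 7.4 | 5.5 |

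*Working forward to the acceptance limits,* with the rest unbiased and high-band bias B, so that mean = fB and SD = √[s² + f(1 − f)B²]:

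| s | f | B | Mean | SD | Below 5 and 8? | Below 6 and 10? |
|---|---|---|---|---|---|---|
| 5.7 | 5% | 20 | 1.0 | 7.18 | yes | yes |
| 5.7 | 10% | 15 | 1.5 | 7.26 | yes | yes |
| 5.7 | 10% | 20 | 2.0 | 8.28 | no | yes |
| 5.7 | 20% | 15 | 3.0 | 8.28 | no | yes |
| 5.0 | 10% | 20 | 2.0 | 7.81 | yes | yes |
| 5.0 | 20% | 20 | 4.0 | 9.43 | no | yes |

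**Is a small share plausible?** This too must be assumed. If SBP were normal with mean 115 to 125 and SD 20 to 22, the 161-180 band would hold about 1% to 5% of points, or roughly 30 to 130 of 2800.

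**A gradual trend instead of a step.** With an assumed SBP SD of 20, a slope of −0.2 mmHg per mmHg centred on the mean leaves pooled bias near zero and contributes 0.2 × 20 = 4.0 mmHg to the SD. The remainder is √(5.70² − 4.0²) = 4.06, so this fits the reported SD. The implied bias at SBP 170 is −0.2 × (170 − 115) = −11 if the mean is 115, or −9 if it is 125.

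**The case against.** A reader might infer that a high-band error would be invisible. The documents do not support that, for three reasons.

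- Bland-Altman plots are the protocol's outcome method. They set the difference against BP level, so a trend such as the one above could be seen. The SAP text does not mention these plots, and its Figure 1 is not available to this review. Whether that figure shows error by level is unknown, and its absence here is not a fault of the plan.
- The SD is also an acceptance limit, and a level-dependent error inflates it. With an SBP SD of 20, a slope of 5.70/20 = 0.285 would by itself use up the whole reported SD. The forward table shows larger errors failing the 8 mmHg limit as the high-band share grows.
- The BP distribution, the share and the slope are all assumed.

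Two further readings also go too far. Section 4 promises that the bands will be covered; it sets no accuracy criterion within each. The SAP's 2800 points are not a random draw but all retained windows, so stratifying the draw in protocol section 13 would leave the SAP analysis unchanged. The SAP text also does not itself claim accuracy in the high band.

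What remains is that a plot without a planned count, bias or slope is not a planned check. Neither sampling rule controls or reports the BP mix. The high-band share is unknown because nothing in the plan asks for it.

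**Conclusion.** The point holds as a gap in analysis and reporting. The coverage promise in section 4 is not verified anywhere, and the SAP text judges accuracy only on pooled figures.

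At an assumed 5% high-band share, a high-band SBP error of about 7 to 12 mmHg, above both of the SAP's mean-error limits, is compatible with the reported result. A 20 mmHg error would still meet the 5 and 8 mmHg limits if the within-band SD were 5.7. At a 10% share and the same SD it would fail the 8 mmHg limit, although at within-band SD 5.0 it would still pass (7.81). Masking is therefore real for a sparse high band and weakens as the share grows. The calculations assume one within-band SD for all bands and, in the forward direction, no bias elsewhere.

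These figures show what the pooled summary cannot exclude. They are not evidence that the device has such an error, nor that the high band was missed.

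**What to change.** In the SAP:

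- Tabulate windows and patients in each SBP and DBP band of protocol section 4, with a row for readings below the low band. State which reading assigns a window to its band.
- Report mean error and SD per band where data exist.
- Regress the difference on the average of the two methods, allowing for repeated measures within patient. Give the slope with its confidence interval, and note that 6 patients make it imprecise.
- Keep the pooled result, but limit the accuracy claim to the bands actually covered, stating how many patients contributed to each.

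Because the SAP already reports results, these additions should be labelled as made after the data were seen.

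The cost is one table and one regression on data already recorded, with no new patients or procedures. The downside is that the claim may become narrower.

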## INVESTIGATOR STUDY PLAN - REQUIRED

A minimum of 30 subjects will be recruited in groups of 5. An analysis of 255 time points per patient will be used to compare ViTrack with arterial line measurements. If the bias exceeds the standards, the algorithm will be further optimized. Subsequently, an additional 5 subjects will be recruited, and the same protocol will be applied so that the correction, if required, may be validated.

### 5. BACKGROUND\*

Currently, there is no standalone, wearable, continuous, non-invasive, accurate BP monitor (cNIBP) available that does not require calibration. Consequently, accurate hypertension diagnosis and management and assessment of 24-hr BP parameters and nocturnal BP have remained elusive.

In addition, there is a need for cNIBP measurement in hospitals, where accurate, continuous BP monitoring requires invasive intra-arterial catheters that lead to complications. In intensive care units and operating rooms, intermittent BP measurements with oscillometric, automatic upper arm cuff-based devices are the only option for non-invasive monitoring.

ViTrack is a wrist device that includes a camera, LED lights, small balloon and soft silicone membrane. The soft medical grade silicone membrane is in contact with the skin. The ViTrack is placed over the radial artery at the wrist with the help of a strap.

The ViTrack will be strapped to the right or left wrist making sure it is comfortable to the subject. A one-time calibration, which takes less than 2 mins, involves gradual increase and decrease of the balloon pressure at a rate standard for conventional BP measurement (4 mmHg/s). The ViTrack balloon is less than 10 cc and sits just over the radial artery. Uniqueness of this setup is the effective isolation of the primary measurement area over the radial artery from the rest of the area under the strap and eliminates the need for a complete cuff around the limb. This unique design enables use of the device on a limb without compromising the venous and lymphatic circulation, and flow in other arteries in the limb. Other clinical studies show that subjects hardly feel the inflation and deflation of the balloon and that the ViTrack is far more comfortable when compared to standard upper arm cuff devices.

During calibration, the optical sensor captures spatiotemporal skin force change as the pressure inside a pneumatic actuator increases and decreases to gently occlude and release the blood vessel. Based on ViTracks proprietary methodology, this force information enables a direct measure of both systolic and diastolic BP (SBP, DBP). After baselining, the optical sensor continuously tracks beat-to-beat SBP and DBP in an isolated small region of skin over the radial artery with minimal contact without the need for a pressure cuff.

The proposed study is the first to compare rigorously the ViTrack to intra-arterial continuous BP monitoring.

## INVESTIGATOR STUDY PLAN - REQUIRED

[figure not shown]

Figure 1. ViTrack components.

Figure 2: ViTrack attached to the wrist.

### 6. Inclusion and Exclusion Criteria\*

#### Inclusion criteria:

- a. Patients between the ages of 18 – 90 years age who are undergoing any surgery or in the intensive care unit and require intra-arterial catheterization for continuous BP measurement.
- b. Patients having elective surgeries.
- c. Patients having emergent surgeries, but only if research staff can have appropriate time to review study with patient and obtain signature on fact sheet prior to administration of medications that could affect coherency.
- d. Patients who are able to review, verbalize understanding, and sign fact sheet and HIPAA authorization. If patient has a health care proxy (HCP) or legal guardian, study will be reviewed, and signature of HCP or legal guardian will be obtained.

## **INVESTIGATOR STUDY PLAN - REQUIRED**

Exclusion criteria:

- a. Inability to obtain consent from the patient, HCP or legal guardian
- b. Greater than 10% difference in BP measurements between both arms prior to surgery
- c. Pregnant women
- d. Prisoners
- e. Inability to insert a radial artery catheter
- f. Any other condition that would increase the risk of participation in the study in the opinion of the site Investigator
- g. Upper extremity arteriovenous hemodialysis shunt
- h. Upper extremity amputation
- i. Surgical position/draping precludes access to the wrist.
- j. Wrist distortion or pain from arthritis
- k. Prior trauma or surgery at the radial artery monitoring site

### **7. STUDY-WIDE NUMBER OF SUBJECTS\***

NA

### **8. STUDY-WIDE RECRUITMENT METHODS\***

NA

### **9. STUDY TIMELINES\***

- a. The duration of an individual subject's participation in the study either in the operating room or intensive care unit will be approximately four hours.
- b. The duration anticipated to enroll all study subjects is approximately 1 year.
- c. The estimated date for the investigators to complete this study (complete primary analyses) is approximately 2 years.

### **10. STUDY ENDPOINTS\***

- a. The primary and secondary outcome measures: accuracy of ViTrack in measuring BP continuously as determined by use of Bland-Altman plots
- b. Any primary or secondary safety endpoints: Observing for local skin irritation

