## **INVESTIGATOR STUDY PLAN - REQUIRED**

A sample size estimate was determined using the Bland-Altman method within MedCalc. Assuming an alpha error of 0.05, a beta error of 0.1, expected mean of differences of 5 mm Hg, expected standard deviation of 10 mm Hg, and maximum allowed differences between methods of 26 mm Hg, we calculated the minimum number of pairs to be 1570 which should be obtained with the number of subjects we propose to study

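### Continuous accuracy is the primary outcome, but no analysis asks whether ViTrack follows each patient's pressure changes, so the reported SDs also fit a device that follows only part of them.

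*Protocol*

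**What the plan says.** Protocol section 10 defines the primary and secondary outcome as "accuracy of ViTrack in measuring BP continuously as determined by use of Bland-Altman plots". Section 5 describes a single short balloon calibration and then states: "After baselining, the optical sensor continuously tracks beat-to-beat SBP and DBP in an isolated small region of skin". Section 11 expects the device's analogue signal to follow the arterial one when calibration is optimal.

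For the analysis, section 13 says "Differences in device readings will be calculated as ViTrack minus arterial line values" and "Bland Altman plots will be used to determine agreement between the two devices", applied to ten-beat averages at randomly chosen points. The sample size in the same section is set on limits of agreement. Section 4 plans pressures from low to high, with SBP bands running from 90 to 180 mmHg. It does not ask for that range within each patient, and no analysis by band is planned.

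The SAP pairs averages over successive 20-second windows, about 2800 in 6 patients, and judges the pooled mean error and SD against <5 and <8 mmHg or <6 and <10 mmHg. It concludes: "ViTrack showed far higher accuracy for both SBP (mean error = 0.19 mmHg [SD = 5.70 mmHg"; for DBP it gives a mean error of 0.90 and an SD of 5.97 mmHg. Its results figure is not available in the text reviewed here.

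**The concern.** A continuous monitor is useful because it shows falls and rises. An error SD on its own cannot show that. It is small when the device follows the pressure, and also when the pressure barely moves and the device responds weakly. The two cases separate only if one knows how much the reference moved within each patient, or compares changes in the device with changes in the reference. Neither document plans either, and the readable text gives no within-patient arterial SD or range. At stake is what the SAP's accuracy statement may be taken to mean: average closeness to the arterial line, or the ability to follow it.

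**Working it through.** **1. The plan's own figure.** Section 13 gives "Assuming an alpha error of 0.05, a beta error of 0.1, expected mean of differences of 5 mm Hg". It takes 10 mmHg for the SD of the differences and 26 mmHg as the largest difference permitted. The upper limit of agreement is 5 + 1.96 × 10 = 24.6, which leaves 26 − 24.6 = 1.4 mmHg. The standard error of a limit is about 10 × √((1 + 1.96²/2)/n) = 17.09/√n. With two-sided alpha 0.05 and power 90%, n ≈ ((1.960 + 1.282) × 17.09/1.4)² ≈ 1566; the non-central t version gives 1568. The stated 1570 pairs reproduces. None of its inputs concerns change within a patient, so the study is sized for absolute agreement only.

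**2. Model for partial tracking.** Let arterial pressure vary around a patient's mean with SD s, and let a noise-free device show a fraction b of each change.

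- Device centred on the patient's mean: error SD = (1 − b)s, so b = 1 − SD/s.
- Device set once at a random time: the error depends on the difference between two pressures, so error SD ≈ √2(1 − b)s and b ≈ 1 − SD/(√2 s).

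The documents do not give s, so 8, 10 and 12 mmHg are assumptions. Example for SBP at s = 10: 1 − 5.70/10 = 0.43, and 1 − 5.70/14.14 = 0.60.

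| Assumed s (mmHg) | b giving SBP SD 5.70, centred | same, calibrated once | b giving DBP SD 5.97, centred | same, calibrated once |
|---|---|---|---|---|
| 8 | 0.29 | 0.50 | 0.25 | 0.47 |
| 10 | 0.43 | 0.60 | 0.40 | 0.58 |
| 12 | 0.52 | 0.66 | 0.50 | 0.65 |

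As an illustration, at s = 12 a 40 mmHg fall in SBP would leave the reading too high by (1 − 0.525) × 40 = 19 mmHg (centred) or (1 − 0.664) × 40 ≈ 13 mmHg (calibrated once).

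**3. Largest s at which a limit L is still met.** This is L/(1 − b) if centred and L/(√2(1 − b)) if calibrated once.

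| Device | SD < 8 | SD < 10 |
|---|---|---|
| Half of each change (b = 0.5) | s below 11.3 to 16 | s below 14.1 to 20 |
| Frozen reading (b = 0) | s below 5.7 to 8 | s below 7.1 to 10 |

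If every patient's SBP swept 90 to 180 mmHg uniformly, s would be 90/√12 ≈ 26. The centred error SD would be 26 for a frozen device and 13 for a half-tracking one, and both would fail the SAP limits.

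**4. Simulation check.** Six patients with 467 windows each (2800/6 ≈ 467), slowly varying pressure, and assumed between-patient SD 15 and device noise SD 3. Ranges run from the centred device to one set at a single calibration point.

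- Half tracking, s = 10: error SD 5.69 to 6.55; the <5 and <8 limits were met in 100% to 90% of runs.
- Half tracking, s = 12: met in 98% to 66.5% of runs.
- No tracking, s = 5: error SD 5.70 to 6.53; met in 100% to 89.5% of runs.
- No tracking, s = 10: met in 2% to 0% of runs.

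The single-point SD exceeded the centred one by less than √2 (6.55/5.69 = 1.15 for half tracking at s = 10), so the two cases in step 2 are best read as a bracket.

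**5. Would a pooled Bland-Altman plot show it?** With between-patient SD B, the slope of difference on average for the centred device is −((1 − b²)/2)s² / (B² + ((1 + b)/2)²s²). For b = 0.5, s = 10 and assumed B = 15 this is −37.5/(225 + 56.25) = −0.13. Within a patient (B = 0) it is −37.5/56.25 = −0.67. Pooling hides most of the slope.

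**The case against.** **The plot is not blind to this failure.** Under-response gives a sloping band within each patient, and section 10 makes the plot the basis of the outcome. That stands in part. But no slope is estimated, no criterion is attached to one, and step 5 shows how far between-patient spread can flatten it.

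**A wide pressure range is planned, and would expose weak tracking.** It would if each patient covered it. Section 4 does not ask for that, and in 6 patients the spread could lie mainly between patients.

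**The missing figure may show the spread.** It may. The statement about variability is limited to the readable text.

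**A reader might infer that a device that does not track at all would pass.** That holds only for small within-patient variation (step 3), and it fails if pressures ranged widely. The documents do not show that these patients were that stable.

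**A reader might also infer that the trial cannot address continuous measurement.** That goes too far. Section 4 sets out to compare continuous readings with the arterial line, section 10 equates accuracy with agreement, and pairs every 20 seconds do bear on it. Tracking is a further question that the recordings can answer.

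**A pass/fail gate on the slope would be hard to defend.** This stands. There are six patients, slopes are imprecise in stable patients, and the reference is the opposite wrist. Section 13's Exclusion criteria counterpart, in section 6, excludes only differences between arms above 10%, so a proportional arm difference alone could move the slope from 1.

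**Conclusion.** The omission is certain in the readable text: the outcome is continuous accuracy, and nothing planned or reported measures within-patient tracking. Its size is conditional, because s is assumed and the same range was used for SBP and DBP. Over s of 8 to 12 mmHg, the reported SDs are compatible with a device showing as little as a quarter to a half of each change (centred) or about a half to two thirds (calibrated once). These are the worst values for a given s, since any noise in the error implies better tracking. The partial-tracking reading holds over a wide range of s; the frozen-reading case is a narrow one. A reader might take this as a sign that ViTrack tracks poorly. The documents do not support that: the same SDs fit a device that tracks well with some noise, and the present analysis cannot separate the two.

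**What to change.** Add to protocol section 13 and the SAP, as supplementary analyses of the paired recordings already made:

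1. For each patient, the SD and range of arterial SBP and DBP.
2. The within-patient slope of ViTrack on arterial pressure, with patient-specific intercepts and a patient-level confidence interval; and concordance of paired changes over a stated lag with a stated exclusion zone for small changes.
3. As a benchmark, the error SD obtained by holding each patient's first post-calibration ViTrack value constant.

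Report these descriptively, noting the opposite-wrist reference and the six patients. Word the SAP conclusion as average agreement unless these results also support tracking.

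The cost is SAP wording and a few hours of analysis, with no new patients. The downside is that the tracking result may look less favourable than the pooled SD.
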